There is an optional open-label substudy in which enrolled subjects may elect to participate at any time from the day of enrolment through Day 85. A separate signed ICF (and separate assent when necessary) will be obtained prior to participation in the substudy. Subjects will be excluded from participating in the substudy if they meet additional exclusion criteria listed in Protocol Section 4.1.2.1. Temporary vaccination holding criteria are to be followed for the Day 85 vaccination.

Up to 120 enrolled subjects may participate in the substudy. The duration of the entire study will not change; however, additional visits/procedures starting on Day 85 will include the following:

- 3 additional visits (Days 92, 99, and 113)
- 1 additional intranasal vaccination (Day 85)
- Up to 3 additional nasal samples, including 2 of those needed for midturbinate/nasopharyngeal sample collection (Days 92 and 99) and 1 needed for leukosorb (Day 113). Subjects will contribute to all Day 85 sampling (systemic and nasal).
- Up to 2 additional blood samples (Days 85, if not already assigned to provide, and 113, including blood for cellular-mediated and systemic immunity responses)
- 1 additional subject diary (subjects to record maximum daily reactogenicity [nasal/respiratory, systemic] in a subject diary for 7 consecutive days starting the day following study vaccination)
- 1 additional test for SARS-CoV-2 within 72 hours prior to Day 85 vaccination.

All subjects participating in the open-label substudy will receive an intranasal re-vaccination/attenuated challenge with BPZE1 on Day 85. Subjects may have the planned re-vaccination/attenuated challenge deferred to a later date (up to 20 days) if pre-defined temporary exclusion criteria in Protocol Section 4.1.2.1 are met or for other personal reasons (eg, holiday, school schedule). Subjects will be monitored for at least 30 minutes after re-vaccination/attenuated challenge, with a post-vaccination evaluation for reactogenicity (nasal/respiratory, and systemic) completed prior to release from clinical observation.

Subjects will receive a subject diary on Day 85. All subjects (with assistance when needed) will record maximum daily reactogenicity in a subject diary for 7 consecutive days starting the day following re-vaccination/attenuated challenge (retrospective of the highest value in the previous 24 hours).

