Data will be presented in the listings as reported. For summaries and analysis, the following conventions apply.

A. Incomplete Start Date:

Missing day and month

- If the year is the **same** as the year of the first dosing date, then the day and month of the first dosing date will be assigned to the missing fields.
- If the year is **prior to** the year of first dosing date, then December 31 will be assigned to the missing fields.
- If the year is **after** the year of first dosing, then January 1 will be assigned to the missing fields.

Missing day only

- If the month and year are the **same** as the year and month of first dosing date, then the first dosing date will be assigned to the missing day.
- If either the year of the partial date is **before** the year of the first dosing date or the years of the partial date and the first dosing date are the same but the month of partial date is **before** the month of the first dosing date, then the last day of the month will be assigned to the missing day.
- If either the year of the partial date is **after** the year of the first dosing date or the years of the partial date and the first dosing date are the same but the month of partial date is **after** the month of the first dosing date, then the first day of the month will be assigned to the missing day.
- If the stop date is not missing, and the imputed start date is after the stop date, the start date will be imputed by the stop date, i.e. set to the stop date.

Missing day, month, and year

- No imputation is needed; the corresponding AE will be included as TEAE if the end date of the AE is after the first dose date or the end date is also missing.

B. Incomplete End Date:

If the imputed stop date is before the start date, then the imputed stop date will be equal to the start date.

Missing day and month

- If the year of the incomplete stop date is the **same** as the year of the last dosing date, then the day and month of the last dosing date will be assigned to the missing fields.
- If the year of the incomplete stop date is **prior to** the year of the last dosing date, then December 31 will be assigned to the missing fields.
- If the year of the incomplete stop date is **prior to** the year of the last dosing date but is the same as the year of the first dosing date, then the first dosing date will be assigned to the missing date.

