- If the year of the incomplete stop date is **after** the year of the last dosing date, then January 1 or EOS date which ever occurred later will be assigned to the missing fields.

Missing day only

- If the month and year of the incomplete stop date are the **same** as the month and year of the last dosing date, then the day of the last dosing date will be assigned to the missing day.
- If either the year of the partial date is **not equal to** the year of the last dosing date or the years of the partial date and the last dosing date are the same but the month of partial date is **not equal to** the month of the last dosing date, then the last day of the month will be assigned to the missing day.

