9.2.2. Relationship of Adverse Events to Vaccination

The relationship of vaccination to TEAE will be characterized using the following criteria:

- Related: There is a reasonable possibility that the study vaccination caused the AE. Reasonable possibility means that there is evidence to suggest a causal relationship between the study vaccination and the AE.
- Not Related: There is not a reasonable possibility that the study vaccination caused the event.

Missing relationship will be counted as related to study vaccination.

All TEAEs through 28 days following first study vaccination and following re-vaccination/attenuated challenge (substudy) will be summarized by relationship to study vaccination, and by treatment group, age group and overall.

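### Partial adverse-event start dates are compared only with the first dose, so a post-challenge event with an unknown day in the challenge month is usually dated before the Day 85 challenge and leaves both 28-day tables

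*SAP*

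**What the plan says.** SAP 4.4 (Handling of Missing Data, incomplete start date) gives these rules when only the day is missing:

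- For a partial date falling in the first-dose month, the rule reads in part: "as the year and month of first dosing date, then the first dosing date will be assigned to the missing day".
- Where the partial date is in an earlier month, the last day of that month is used.
- If it is in a later month, "then the first day of the month will be assigned to the missing day".
- A final check begins "If the stop date is not missing, and the imputed start date is after the stop date", and in that case the start is set to the stop date.

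No start-date rule mentions the second dose. The incomplete end-date rules in the same section do: in the month of the last dose, "then the day of the last dosing date will be assigned to the missing day". So the SAP distinguishes the two doses but uses the second only for stop dates.

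Several outputs depend on the onset date. SAP 9.2.2 states: "All TEAEs through 28 days following first study vaccination and following re-vaccination/attenuated challenge (substudy) will be summarized". SAP 9.2.3 plans the same pair of 28-day tables by severity. SAP 9.2 adds a substudy summary from Day 85 to end of study, and an overall summary from Day 1 to end of study. Medically attended events are summarized through 84 days after any vaccination.

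SAP 3.1 has up to 120 subjects receiving the challenge on Day 85, with deferral of up to 20 days allowed. Neither SAP section 11 nor the protocol supplies a rule that alters the start-date imputation.

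**The concern.** Safety after the challenge is a separate stated evaluation: both documents require it to be described apart from safety after the first vaccination. Whether an event enters it depends on onset relative to the challenge. The later-month rule makes no reference to the challenge, so it pulls an event from the challenge month back to the 1st, ahead of the dose it may have followed.

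The final check against the stop date cannot repair this, because it only ever moves a start date earlier.

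The imputed date also sits awkwardly with the collection schedule. Under protocol 6.3.5.2, ordinary unsolicited events are collected for 28 days after a vaccination. Between Day 29 and the challenge, collection is essentially limited to medically attended events, events of special interest, serious events and events that delay a vaccination. An ordinary adverse event recorded in the challenge month is therefore very likely post-challenge, yet the rule places it in a period when it would not have been collected. At stake is an undercount in the tables meant to show tolerability of a second live dose in children.

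**Working it through.** The documents give no figure to reproduce here. The check applies the SAP rule to calendar dates.

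**Inputs**

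- Challenge date = first dose + 84 days + deferral of 0 to 20 days (SAP 3.1), that is Day 85 to Day 105.
- True onset = 0 to 28 days after challenge (SAP 9.2).
- Imputed start when the day is missing = 1st of the onset month (SAP 4.4). Onset is never in the first-dose month.
- First 28-day window: Day 1 to Day 29. Second: challenge date to challenge date + 28 days.
- Assumption: all dates are equally likely. This affects only the percentages.

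**Where the imputed date lands.** For an onset in the challenge month, the imputed date is the 1st of that month. It precedes the challenge by 0 to 30 days.

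- Earliest: Day 85 − 30 = Day 55.
- Latest that still precedes the challenge: Day 105 − 1 = Day 104.

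Day 55 is after Day 29, so an event moved before the challenge is in neither 28-day window. If the challenge was on the 1st, the imputed date equals the challenge date and the event is kept.

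**Example.** First dose 1 March 2023, challenge 24 May 2023, event recorded as May 2023. The imputed start is 1 May, which is 61 days after the first dose, or Day 62. That is after Day 29 and before the challenge on Day 85.

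**How often.** Enumerating every first-dose date over four years (1,461), every deferral (21) and every onset day (29) gives 1,461 × 21 × 29 = 889,749 cases.

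| Quantity | Count | Share |
|---|---|---|
| Onset in the challenge month | 480,501 | 480,501 / 889,749 = 54.0% |
| Of these, imputed before the challenge | 451,332 | 451,332 / 480,501 = 93.9% |
| Of these, kept (challenge on the 1st) | 29,169 | 29,169 / 480,501 = 6.1% |
| Lost from both 28-day tables, of all cases | 451,332 | 451,332 / 889,749 = 50.7% |
| Onset in the following month, all kept | 409,248 | 409,248 / 889,749 = 46.0% |

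No case enters the first-vaccination 28-day table. Under the SAP rule 100% − 50.7% = 49.3% stay in the correct table. If the challenge date is imputed for challenge-month events, all 889,749 stay.

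**Other outputs.** With the challenge on Day 85 itself, the imputed date is Day 55 to 84. The event then also leaves the Day 85-to-end-of-study summary, and a medically attended event is credited to the first vaccination's 84-day window, which ends on Day 85. With a deferred challenge the imputed date can fall after Day 85. For example, first dose 1 March 2023 and challenge 13 June 2023 (deferred 20 days) give 1 June, or Day 93. Such an event leaves the substudy summary if that summary starts at the actual challenge, but not if it starts at study Day 85 taken literally. It would then lie outside the first vaccination's 84-day window as well as before the challenge.

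**The case against.** The strongest case against is that this will rarely matter. Protocol 6.3.5.3 requires start and stop dates for each event. Reactogenicity in the 7 days after challenge comes from a daily diary. Substudy visits on Days 92, 99 and 113 make a missing onset day easy to query. The documents give no rate of partial dates, at most 120 subjects are exposed, and no primary comparison uses these tables. All of that stands and sets the size of the point. It does not make the rule correct for the records that do occur.

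Four stronger readings are tempting, and the documents do not support them.

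- *Every day-missing event in the challenge month is misassigned.* Medically attended, special-interest and serious events are collected continuously, and events that delay a vaccination are recorded too (protocol 6.3.5.2). When such an event began before the challenge, the 1st of the month puts it in the right period.
- *The events vanish from reporting.* They stay in the overall Day 1-to-end-of-study summary, and SAP 4.4 presents dates in listings as reported. Serious events also have a detailed listing with vaccination and event dates.
- *Year-only dates drop out the same way and need the same fix.* A year-only event in the first-dose year is set to the first dosing date, so it enters the first-vaccination table. That is a different error. Imputing the challenge date whenever the year matches would move events that may have followed the blinded, randomized first dose into the open-label challenge table.
- *The stop-date rules are equally faulty.* Their directions do differ: the last dosing date in one case, and "January 1 or EOS date which ever occurred later will be assigned to the missing fields" in another. But the latter applies only when day and month are both missing. Outside the last-dose month, a missing stop day becomes the last day of the month. Duration is summarized only for reactogenicity events (SAP 9.1), not for unsolicited events generally. This is largely a matter of preference.

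**Conclusion.** The point holds for one case: a post-challenge adverse event whose month is known to be the challenge month and whose day is missing. Followed as written, SAP 4.4 dates it before the challenge unless the challenge fell on the 1st, and removes it from both 28-day tables. With uniform dates, deferral of 0 to 20 days and onset 0 to 28 days after challenge, this affects about 94% of challenge-month onsets and about 51% of all post-challenge onsets with a missing day. Reading the Day 85-to-end-of-study summary as starting at the challenge, the same events leave that summary too.

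The error runs against detecting harm from the second dose, so it is not conservative. Its practical weight is small, because few such records are expected and the primary endpoint is not involved. It is worth correcting mainly because the correction is simple.

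**What to change.** Add one rule to the incomplete start-date section of SAP 4.4. For substudy subjects who received the challenge, when only the day is missing and the month and year match the challenge, impute the actual challenge date. Make two exceptions:

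- the stop date is before the challenge; or
- other recorded information shows onset before the challenge, such as the event being the reason for a vaccination delay or being first recorded at a visit before the challenge.

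Leave the year-only start-date rules and the stop-date rules as they are. It would help to state in SAP 9.2 that Day 85 in the substudy summary means the actual challenge date, since the challenge may be deferred.

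The cost is a few lines of SAP text and programming. There is a small downside: a few medically attended, special-interest or serious events that began before the challenge, with nothing recorded to show it, would be attributed to the challenge. For a safety table that is the conservative direction.

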6.3.5.2 Assessing and Documenting Adverse Events

Safety will be assessed by the frequency and severity of:

1. All AESIs and SAEs occurring from the time of vaccination through Day 169/EOS.
2. All MAAEs occurring through 84 days following any vaccination.
3. Solicited reactogenicity events occurring from the time of any study vaccination for 7 consecutive days starting the day following study vaccination, including:
 - a. Nasal/respiratory reactions (runny/congested nose, sore/irritated throat, cough, sneeze, nasal or sinus pain/irritation, difficulty breathing/wheezing; if epistaxis occurs it should be listed as an AE);
 - b. Systemic reactions (fever, headache, fatigue/malaise, loss of appetite/anorexia, vomiting, diarrhoea, nausea, myalgia, acute allergic reaction/urticaria); and
 - c. Local reactions (pain/tenderness, redness, swelling [after IM injection only]).
4. Unsolicited AEs – all AEs regardless of causality, will be collected for 28 days after any vaccination. Between screening (signing of ICF) and Day 1, AEs will be collected if classified as serious or if considered related to study procedure or study involvement. Any event that results in vaccination delay (eg, temporary exclusions due to acute upper respiratory symptoms/illness or fever, or investigator determined medical condition) during screening or during study conduct will also be recorded as an AE. Should any reactogenicity event extend beyond 7 days following vaccination, it will be recorded as an AE with the same start date as the reactogenicity event and followed until considered resolved.

At every study visit, subjects will be asked a standard non-leading question to elicit any medically related changes in their well-being that would pertain to the AEs being collected at the time. They will also be asked if they have been hospitalized, had any accidents, used any new medications, received a vaccination or changed concomitant medication regimens (both prescription and OTC medications).

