Duration through 7 days following study vaccination and duration through resolution following study vaccination will be summarized using descriptive statistics. Duration through 7 days is defined as days with the reactogenicity event onset through 7 days following vaccination per patient reported daily diary. Duration beyond 7 days is defined as days with the reactogenicity event continuing beyond 7 days as captured in adverse events.

Solicited AEs will be reported separately using the same methods above following study vaccination on Day 85 in the substudy.

Table 9-1-1 Local Reactogenicity Grading Scale

Variable	Grade 1	Grade 2	Grade 3
Pain/tenderness ^a	Easily tolerated, causes no or minimal limitation of use of limb	Sufficiently discomforting, interferes with greater than minimal limitation of use of limb	Causing inability to perform usual social and functional activities
Redness ^{b,c}	Evidence of redness that is ≤ 2.5 cm in diameter	>2.5 cm in diameter with $<50\%$ of upper extremity surface area segment involved	$\geq 50\%$ upper extremity surface area segment involved OR ulceration OR infection OR phlebitis OR sterile abscess OR drainage
Swelling ^{b,c}	Evidence of swelling that is ≤ 2.5 cm in diameter	>2.5 cm in diameter with $<50\%$ of upper extremity surface area segment involved	$\geq 50\%$ upper extremity surface area segment involved OR ulceration OR infection OR phlebitis OR sterile abscess OR drainage

Note: Local reactogenicity to be evaluated after an IM injection only. Grade 0 will be the classification if the observation is less than a grade 1. Any grade 3 reactogenicity event that leads to an unscheduled visit to a healthcare provider will be recorded as an MAAE.

^a To be graded by investigator based on subject diary.

^b Grade to be applied by data management based on measurement recording unless grade 3 is noted with other characteristics by the investigator.

- c If redness or swelling exceeds 100 mm or >50% of upper extremity surface area, or involves the shoulder, elbow, or chest, or prevents everyday activity, then subjects must be evaluated and a swelling assessment eCRF will be completed.

Source: Adapted from DAIDS Version 2.1, 2017.

Table 9-1-2 Nasal/Respiratory Reactogenicity Grading Scale

Variable	Grade 1	Grade 2	Grade 3

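### A partial stop date that matches the dosing month or year is set to the last dosing date, so a reaction known to have outlasted the diary week can be summarised as lasting 1 day

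*SAP*

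**What the plan says.** SAP 4.4 gives conventions for partial AE and medication dates in summaries and analysis; listings show dates as reported. Part B, on incomplete end dates, says:

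- Day missing, month and year as for the last dose: "then the day of the last dosing date will be assigned to the missing day".
- Day missing, any other month or year: "then the last day of the month will be assigned to the missing day".
- Day and month missing, year as for the last dose: "then the day and month of the last dosing date will be assigned to the missing fields".
- Day and month missing, year before the last dose: 31 December. If that year is also the year of the first dose, a further bullet says "then the first dosing date will be assigned to the missing date".
- Day and month missing, year after the last dose: "then January 1 or EOS date which ever occurred later will be assigned to the missing fields".
- Floor: "If the imputed stop date is before the start date, then the imputed stop date will be equal to the start date".

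These rules reach solicited reactions through Protocol 6.3.5.2. When a reaction extends past 7 days after vaccination, "it will be recorded as an AE with the same start date as the reactogenicity event". SAP 9.1 takes the 7-day duration from the diary. It also summarises duration through resolution, and for the later part states: "Duration beyond 7 days is defined as days with the reactogenicity event continuing beyond 7 days as captured in adverse events".

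Main-study children are dosed on Day 1 only (SAP 3.3). Substudy children have a second dose on Day 85, which may be deferred by up to 20 days (SAP 3.1).

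**The concern.** In the main study the last dose is Day 1, and no post-vaccination event can start before it. An imputed stop on that date therefore never falls after the start, and the floor then makes the two equal. A carried-over reaction is on the AE form precisely because it was still present after the diary week, yet it would be summarised as ending on the day it began. Nothing in part B uses that known persistence.

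In the substudy the last dose is the challenge, and no rule ties an event to the dose it followed. A reaction to the first vaccination can then take its stop date from an unrelated later dose. How long reactions persist is safety information worth summarising correctly, in what SAP 3.1 describes as the first study of BPZE1 in school-age children.

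**Working it through.** The plan states no figure for this point, so the check applies the rules as written. Duration = stop − start + 1.

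**Worked example.** Dose 7 March (Day 1), start 9 March (Day 3). The diary covers Days 2 to 8 (8 to 14 March). The reaction is still present on Day 9 (15 March), so the certain minimum is 9 to 15 March = 7 days. The substudy dose on Day 85 is 7 March + 84 days = 30 May.

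| Child | Stop date recorded | Imputed stop | Duration |
|---|---|---|---|
| Main study | March, day missing | 7 March, floored to 9 March | 1 day |
| Main study | year only | 7 March, floored to 9 March | 1 day |
| Substudy | March, day missing | 31 March | 23 days |
| Substudy | year only | 30 May | 23 + 30 + 30 = 83 days |

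If the substudy dose is deferred to Day 105, the last row becomes 105 − 3 + 1 = 103 days. If duration beyond 7 days is computed as days after Day 8, the main-study rows give 9 March − 14 March = −5, or zero if truncated.

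**Doses in different years.** First dose 20 November, start 22 November, Day 85 on 12 February, stop recorded as the November year only. Two bullets apply. The 31 December bullet gives 9 + 31 = 40 days. The first-dosing-date bullet gives 20 November, floored to 22 November, which is 1 day.

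**How often the bullets apply, given a partial stop date.** The rules were run over every Day 1 date in one calendar year, for starts on Day 1, 2 or 4 and true durations of 8, 10, 14 or 21 days. These inputs are assumptions. The case starting on Day 1 and lasting 8 days ends on Day 8, would not be carried over, and is left out here.

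- Main study, day missing: the stop falls in the dosing month, and the result is exactly 1 day, for 24% to 74% of dosing dates (67% for start Day 2, true 10 days). The rest go to month end and give 26 to 51 days.
- Main study, year only: 1 day for 94% to 98% of dosing dates; the rest go to EOS and give 166 to 169 days.
- Substudy, first-vaccination event, year only: stop at Day 85 for 79% to 83%, giving 82 to 85 days. The other 17% to 21% get 1 day if the first-dosing-date bullet takes precedence.
- Substudy, first-vaccination event, day missing: always month end, never Day 85.

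These percentages are conditional on the date being partial. They are not shares of all events.

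**The case against.** The strongest reply is that little is touched. The listed secondary endpoint is duration during the 7 days after vaccination (Protocol 2.2, SAP 3.2.2.5). SAP 9.1 takes it from the diary, so part B does not reach it. The protocol asks for start and stop dates for every AE (6.3.5.3), follow-up to resolution or stability (6.3.5.8) and data cleaning (8.1), so partial stop dates may be few. No hypothesis test changes. All of this stands, and it keeps the point small. It does not make a 1-day value right for an event known to have lasted longer.

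A reader might go further in four ways that the documents do not support:

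- *Every partial stop date goes to the last dose.* Only those matching its month and year, or its year, do; other day-missing dates already go to month end.
- *A carried-over reaction must itself have lasted more than 7 days.* Protocol 6.3.5.2 counts from vaccination, so a cough from Day 7 to Day 9 is carried over after 3 days.
- *The day-missing rule stretches substudy events to Day 85.* The stretch comes mainly from the year-only rule. The day-missing rule reaches Day 85 only if the recorded stop month is the month of that dose.
- *Duration summaries will differ by substudy participation rather than by vaccine.* Identical records can be imputed differently, as the table shows, but the number of such records is unknown. Lengthening is not general either: reactions after the Day 85 dose shrink to 1 day as in the main study.

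It can also be said that the two overlapping year bullets read naturally as a rule and its exception. That is plausible, but the SAP does not state the precedence.

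**Conclusion.** The point holds in limited form. When the last dose is the dose the reaction followed (main study, or after the Day 85 dose) and the recorded month and year, or the year alone, match it, the rule always returns 1 day. For a carried-over reaction the record can contradict that value: 1 day against a certain minimum of 7 in the example. A first-vaccination event in a substudy child with only the stop year recorded is set to the challenge date when the years match, 83 days in the example. When the doses straddle a new year, two bullets give different dates.

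The affected outputs are the descriptive summaries of duration through resolution and duration beyond 7 days. The size in the final tables depends on the number of partial stop dates, which the documents do not give. This is a minor correction, worth making because the rule is wrong for known cases and cheap to change.

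**What to change.** Amend SAP 4.4, part B:

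1. For a reaction carried over as an AE, set a floor for the imputed stop at the first day after the 7-day diary of the dose it followed (Day 9 for the Day 1 dose).
2. When only the day is missing and the month is the dosing month, use the last day of that month, as the SAP already does for other months. Cap it at the EOS or last contact date, and never place it before the start.
3. Do not use a later dose's date as the stop of an event that followed an earlier dose. Show year-only stop dates in listings and leave them out of the duration summaries, apart from the floor in item 1.
4. Keep one of the two overlapping year bullets.

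Imputing year-only dates as 31 December capped at EOS is not recommended. In the example, Day 169 is 22 August, which gives 23 + 30 + 31 + 30 + 31 + 22 = 167 days and merely replaces one bias with another.

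The cost is a short SAP edit and a change to the date macro, with no change to data collection. Some imputed durations become longer: the main-study example with the day missing moves from 1 to 23 days, which may overstate the true length.
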